7.2.3. Exploratory Endpoint Analyses

- Sustained remission at week-36, measured by the mean change in PASI score from week-24 to week-36, will be analyzed for statistical significance using a paired, two-tailed Student's t-test.
- Treatment response, as measured by PASI 50, will be stratified by CARD14 germline mutations. The proportion of subjects with a PASI 50 response with and without CARD14 mutations will be reported and compared for statistical significance using an unpaired, two-tailed Student's t-test.
- Epithelial expression of CARD14 will be assessed qualitatively by a trained dermatopathologist who is blinded to the biopsy collection time (before or after therapy).
- The gene expression level from the tissue biopsy, before, 4 weeks, and 24 weeks after treatment, will be analyzed for statistical significance using a pared, two-tailed Student's t-test and also compared with normal and psoriatic skin using a two-tailed, two-sample Student's t-test with unequal variance adjusted for multiple comparisons.
- The cytokine level from serum before, 4 weeks, and 24 weeks after treatment, will be analyzed for statistical significance using a pared, two-tailed Student's t-test and also compared with normal and psoriatic serum using a two-tailed, two-sample Student's t-test with unequal variance adjusted for multiple comparisons.

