3.2.2. Secondary Endpoints Assessed by Investigator

- Time to improvement by 50% in the PASI score (PASI 50)
- Mean reduction in body surface area (BSA) at week-24. BSA is collected as part of the PASI assessment tool.
- Proportion of subjects achieving a Physician's Global Assessment (PGA) of 0 or 1 at week-24
- Proportion of subjects achieving a Palmoplantar Physician's Global Assessment (PPPGA) of 0 or 1 at week-24. Palmoplantar disease will be assessed separately from overall disease since it has high morbidity and may respond differently to therapy.
- Mean percentage improvement in nail involvement measured by Nail Psoriasis Severity Index (NAPSI) at week-24. The Nail Psoriasis Severity Index (NAPSI) (24) will be used for evaluating the fingernails and toenails of subjects with PRP. This is expected to be useful tool because nails in PRP have many overlapping features with psoriasis including nail plate crumbling, splinter hemorrhages, nail oil drop (yellow-brown) discoloration, and nail bed hyperkeratosis, although PRP nails are less likely to have onycholysis and red spots in the lunula (25).

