3.2.3. Secondary Endpoints Assessed by Subject

 Proportion of subjects achieving a 4-point improvement in quality of life measured by the Dermatology Life Quality Index (DLQI) at week-24, proportion of patients achieving a DLQI of 0 or 1 at week-24, and mean improvement in DLQI score at week-24. The DLQI (26) is a validated tool for inflammatory skin conditions. It is a 10-question survey, scored 0 – 30 points. For inflammatory skin conditions, a 4-point change in DLQI score is considered clinically important (27).

- Mean percentage in improvement in Psoriasis Symptoms and Signs Diary (PSSD) at week-24, and proportion of patients achieving a PSSD of zero at week-24. The PSSD is an 11-question 0 – 10-point numeric rating scale (NRS) patient-reported outcome measure assessing itch, dryness, cracking, skin tightness, scaling, shedding or flaking, bleeding, burning, stinging, and pain over the last 24 hours and 7 days respectively (28).
- Mean change from baseline individual PRP Area and Severity Index (iPRPASI) at week-24 after treatment with guselkumab, and correlation of subject-assessed iPRPASI scores with investigator-assessed PASI scores. The IPRPASI is a novel subject self-assessment score of disease involvement and severity, based on a previously published similar tool validated for psoriasis (29).
- Sustained remission at week-36, 16 weeks after the last guselkumab dose, as measured by the mean change in PASI from week-24 to week-36. Sporadic PRP is often a self-limited disease, resolving spontaneously after an average of 3-6 years. Other immunomodulatory medications have induced sustained remission of PRP (22), so there is a potential that treatment may "reset" the immune response and lead to long-term improvement in the disease, especially in subjects without genetic mutations. Subjects will be treated with guselkumab as per the FDA-approved psoriasis treatment guidelines, and therapy will be stopped after the 20-week dose. Subjects will be monitored at 24 weeks (primary study endpoint) and then at 36 weeks to assess for sustained remission versus relapse.

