5.1.10. Visit 7 / Week-36 (56 days +/- 7 days after last visit)

Visit 7 will be performed at OHSU or optionally by telemedicine and REDCap survey for subjects who live >30 miles from OHSU.

- Study personnel will gather the following information from the subjects and record the results in REDCap:
 - Change in medications since the last visit
 - Change in drug allergies since the last visit
 - Change in personal or family medical history, including adverse events, since the last visit
 - Weight (performed by the subject for videoconferencing visits)
 - Blood pressure (performed by the subject for videoconferencing visits)
 - Pulse (performed by the subject for videoconferencing visits)
- Subjects will enter the following information about their disease and medical history via OHSU REDCap survey:
 - DLQI
 - PSSD
 - iPRPASI
- The subject will be clinically examined by an investigator (clinician or research nurse, either in-person or via telemedicine) who will assess the following:
 - Full body skin exam with documentation of PASI, PGA, and PPPGA

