7.2. Statistical Analysis Plan

Data analysis will be ongoing throughout the trial by the PI and is expected to be complete within 3 months after the last-subject last-visit.

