7.2.1. Primary Endpoint Analysis

• Mean improvement from baseline PASI at week-24 will be analyzed for statistical significance using a paired, two-tailed Student's t-test.

7.2.2. Secondary Endpoint Analyses:

- Time (weeks) to improvement by 50% in the PASI score (PASI 50) will be reported as a mean with standard deviation and also represented graphically.
- Mean improvement from baseline BSA at week-24 will be analyzed for statistical significance using a paired, two-tailed Student's t-test.
- The proportion of subjects achieving a Physician's Global Assessment of 0 or 1 at week-24 will be reported as a proportion, and compared with historical estimates of treatment success with acitretin and methotrexate (1).
- The proportion of subjects achieving a Palmoplantar Physician's Global Assessment of 0 or 1 at week-24 will be reported as a proportion.
- The mean improvement in nail involvement measured by NAPSI (see below) at week-24 will be analyzed for statistical significance using a paired, two-tailed Student's t-test.
- The proportion of subjects achieving a 4-point improvement in DLQI and the proportion of subjects achieving a DLQI score of 0 or 1 at week-24 will be reported as proportions. The mean

improvement in DLQI score from week-0 to week-24 will be analyzed using a paired, two-tailed Student's t-test.

• The mean improvement in PSSD at week-24 will be analyzed for statistical significance using a paired, two-tailed Student's t-test. The proportion of subjects achieving a PSSD of zero at week-24 will be reported as a proportion.

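### Sustained remission is analysed only as an all-subject mean PASI change from week 24 to week 36, so the plan does not report how many week-24 responders kept their response

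*Combined protocol and SAP*

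**What the plan says.** Section 3.2.3 states what the last visit is for: "Subjects will be monitored at 24 weeks (primary study endpoint) and then at 36 weeks to assess for sustained remission versus relapse". The reason it gives is that treatment might bring lasting improvement after dosing ends. It defines the endpoint as follows: "Sustained remission at week-36, 16 weeks after the last guselkumab dose, as measured by the mean change in PASI" between weeks 24 and 36. Section 7.2.3 repeats this definition and adds the test: "Sustained remission at week-36, measured by the mean change in PASI score from week-24 to week-36, will be analyzed for statistical significance".

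Neither section limits the analysis to subjects who had responded by week 24. No section gives a criterion for remission, relapse or maintained response.

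The plan does have a responder criterion, but applies it at one visit only. Section 3.2.2 lists "Proportion of subjects achieving a Physician's Global Assessment (PGA) of 0 or 1 at week-24", and section 7.2.2 says the Physician's "Global Assessment of 0 or 1 at week-24 will be reported as a proportion, and compared with historical estimates". The PPPGA, DLQI and PSSD proportions are also set at week 24. The PASI 50 proportion by CARD14 status in section 7.2.3 has no stated time point and does not concern retention.

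The data for a retention count will exist. PASI and PGA are recorded at week 24 (section 5.1.9), and section 5.1.10 requires at week 36: "Full body skin exam with documentation of PASI, PGA, and PPPGA".

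**The concern.** Remission versus relapse is a question about individual subjects: of those who were well at week 24, who was still well at week 36? A mean change over everyone treated answers a different question, namely whether the group's average PASI moved.

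Three things follow.

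- Zero change has two opposite meanings. In a subject who is clear it means that remission was kept; in a non-responder it means continuing active disease. The mean treats them alike.
- The test has no result that stands for success. Failure to reject zero change is not evidence of stability. A significant worsening does not say how many relapsed, or whether those who worsened had ever responded.
- The week-24 results do not fill the gap. They say how many subjects were clear or almost clear at that visit, not what became of those same subjects.

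A reader of the planned outputs would know the number responding at week 24 and the average PASI movement afterwards, but not how many responses lasted. That number is what the 12 weeks of follow-up after week 24 are for.

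**Working it through.** **The plan's own figures.** The documents give no effect size, SD or power for the week-36 endpoint. The only power figures, in section 7.1, are for the primary endpoint. For n = 10, mean change 8 and SD 8, the noncentrality is (8/8) × √10 = 3.162 on 9 degrees of freedom. Two-sided power at 0.05 is then 0.8031, as stated. The other nine rows also reproduce to within 0.0001. There is no error there, and none of it bears on week 36.

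**Illustration 1: same mean and p-value, different retention.** From the plan: n = 15. Assumed: 9 of 15 at PGA 0 or 1 at week 24; k = 3 subjects worsen by 20 PASI points; the other 12 do not change; no measurement noise. This is idealised and is not a forecast.

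- Mean change = 3 × 20 / 15 = +4.0.
- SD = 20 × √[k(n − k) / (n(n − 1))] = 20 × √(36/210) = 8.28.
- Standard error = 8.28 / √15 = 2.14.
- t = 4.0 / 2.14 = 1.87 on 14 degrees of freedom, p = 0.082.
- 95% CI = 4.0 ± 2.145 × 2.14 = -0.6 to 8.6.

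Nothing in this calculation depends on which three subjects worsened:

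| | Who worsens by 20 | Mean change (95% CI) | p | Responders kept (exact 95% CI) |
|---|---|---|---|---|
| Cohort A | three week-24 responders | +4.0 (-0.6 to 8.6) | 0.082 | 6/9 (30% to 93%) |
| Cohort B | three week-24 non-responders | +4.0 (-0.6 to 8.6) | 0.082 | 9/9 (66% to 100%) |

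The two cohorts can have identical week-24 data, so adding the planned week-24 summaries does not separate them.

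**Illustration 2: significance does not track retention.** Assumed: 10 subjects, each with baseline PASI 24 and week-24 PASI 6. All are PASI 50 responders, and each remains one while PASI is 12 or lower.

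- All ten worsen by 3 to 5 points. Mean +4.0, SD 0.94, t = 4.0 / (0.94/√10) = 13.4, p = 0.0000003. All 10 keep PASI 50.
- Seven do not change; three worsen by 13, 13 and 14. Mean +4.0, SD 6.45, t = 4.0 / (6.45/√10) = 1.96, p = 0.08. Seven of 10 keep PASI 50.

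The mean is the same. The highly significant result belongs to the cohort in which nobody lost response.

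**The case against.** The strongest case against is one of weight. This is an uncontrolled pilot of 15 subjects, the endpoint is at most secondary, and PASI and PGA are held for both visits. A listing could therefore be added at reporting with nothing lost. The illustrations are constructed: cohort B needs non-responders to worsen while every responder stays flat. No section says that a non-significant p-value will be declared to be remission.

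Much of this stands. The examples show what the statistic cannot distinguish, not what is likely to happen, and misreading a null result is a risk rather than a stated intention. A count added later is weaker than a planned one, however. Section 7.2 says "Data analysis will be ongoing throughout the trial by the PI", and the trial is open label, so a threshold chosen afterwards could follow the data.

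A second fair point is that a PGA cut-off has faults of its own. Week 24 is in person for everyone (section 5.1.9). Week 36 may be by video for subjects living more than 30 miles away (section 5.1.10), and at either visit the assessor may be a clinician or a research nurse. A one-grade shift due to mode or rater could be counted as lost response. This stands, and the fix has to allow for it.

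A reader might also infer that the t-test is too weak to notice infrequent relapse, say 3 of 15 or fewer. The documents do not support that. With 3 relapses of 20 points, exactly zero average drift in the other 12 and noise SD 1 to 4, simulated detection is 2% to 18%. Let the other 12 drift by +1 point and it is 92%, 70% and 48% at SD 1, 2 and 4. Relapse size matters as well: with 5 of 15 relapsing and no drift, detection is 77% to over 99% for 20-point relapses, but 93%, 67% and 37% (SD 1, 2, 4) for 8-point relapses. The plan gives no relapse size, drift or SD, so no detection threshold can be attributed to the test.

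**Conclusion.** The concern holds as a mismatch between question and analysis. Followed as written, the plan tests whether average PASI moved after week 24 and does not report how many week-24 responders kept their response. This follows from the definitions in sections 3.2.3 and 7.2.3 and needs no numerical assumption. The size shown, 6/9 or 9/9 retained behind one identical result, rests on the assumed 9 responders, 20-point worsening and absence of noise, and is illustrative only.

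No claim is made about the power of the t-test, and the primary analysis is not touched. The documents do not equate PGA 0 or 1 with remission; it is simply a criterion that the plan already uses. The change is a worthwhile, inexpensive improvement to a non-primary endpoint.

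Two other inconsistencies are separate and add no weight here: the endpoint's tier (secondary in 3.2.3, exploratory in 7.2.3) and the interval to the last visit (5.1.10 against 3.2.3). Those passages should be reconciled in their own right.

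**What to change.** Amend sections 3.2.3 and 7.2.3 as follows.

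1. Among subjects meeting a criterion already in the plan at week 24 (for example PGA 0 or 1), report the number and proportion still meeting it at week 36, with an exact 95% CI. The investigators should confirm the threshold before any week-36 data are analysed. Count a missing week-36 visit as not maintained; section 8.7.2 allows for no further assessments after consent is withdrawn. Identify week-36 visits carried out early under section 5.2.
2. List each subject's PASI and PGA at weeks 24 and 36, and show whether the week-36 visit was in person or by telemedicine, so that a one-grade change can be told from full relapse.
3. Keep the mean PASI change with its 95% CI as a descriptive supplement, and state that a non-significant p-value will not be read as remission.

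Cost: no new assessments or visits. Because an endpoint definition changes, section 10.6 requires an amendment approved by the funder and then the IRB. The denominator will be small and the interval wide. With 9 responders, each subject moves the estimate by 1/9, or 11 percentage points, and the cut-off stays sensitive to visit mode and rater. The gain is interpretability, not precision.

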3.2.4. Exploratory/Mechanistic Endpoints

- Treatment response, as measured by PASI 50, stratified by the presence or absence of germline CARD14 mutations. Genetic CARD14 gain-of-function mutations were identified in 3 families with familial PRP as well as 12.5% of individuals with sporadic PRP (3). Genetic CARD14 mutations will be measured in study subjects and associated with treatment response to guselkumab. Additionally, de-identified samples will be stored indefinitely for future analysis of genes associated with PRP.
- Normalization of CARD14 epithelial expression at week-24. Despite the fact that not all patients with PRP have genetic CARD14 mutations, immunohistochemical staining of CARD14 in 6 of 6 biopsies from sporadic cases of PRP without germline genetic mutations showed increased expression of CARD14 in the keratinocyte spinous and granular layers of the epidermis (2). CARD14 is thought to act in a synergistic manner with IL-17, activating the transcription factor NF-kB. NF-kB activation was shown *in vitro* to stimulate IL-36gamma, which may induce an amplifying feedback loop from IL-23 to IL-17 and back again (6). Cutaneous biopsies will be obtained from subjects before and 24 weeks after treatment with guselkumab. Inhibition of IL-17 by guselkumab is expected to lead to normalization of CARD14 expression by keratinocytes.
- Normalization of cutaneous gene expression at weeks 4 and 24. Upregulation of Th17 cytokines (IL-17A, IL-17F, IL-22) and pro-inflammatory innate cytokines (TNF, IL-6, IL-12, IL-23, IL-1beta) compared to normal skin were observed in lesional skin from 3 subjects with PRP (5). In order to better understand the inflammatory pathways involved in PRP, lesional and non-lesional biopsies will be obtained from subjects at week-0 prior to the first dose of guselkumab, week-4, and week-24. Cutaneous gene expression of the epidermis and dermis will be analyzed by RNA Sequencing (RNA-Seq and therapeutic response to guselkumab is expected to correlate with normalization of epidermal cytokine levels. De-identified tissue samples will be stored indefinitely for analysis.
- Change in serum cytokine levels at weeks 4 and 24. Serum levels of multiple cytokines have been shown to correlate with disease activity in patients with psoriasis (*30*) but these have not been investigated in patients with PRP. Serum cytokine levels before and after treatment with guselkumab will be analyzed by multiplexed bead-based immunoassay.

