4.2. Exclusion criteria

- Known malignancy or lymphoproliferative disease (except treated basal cell skin cancer, treated squamous cell skin cancer, or treated cervical carcinoma in situ) for at least 5 years.
- Active, untreated, acute or chronic infection, or immunocompromised to an extent that such that participation in the study would pose an unacceptable risk to the subject.
- Positive for human immunodeficiency virus, hepatitis B virus, or hepatitis C virus.
- Have latent or active untreated tuberculosis (TB), a positive QuantiFERON-TB Gold test result, signs or symptoms of active TB on medical history or physical examination, or close contact with a person with active TB and have not undergone evaluation or treatment for TB. Those who are currently undergoing treatment or who have documented completed treatment for active or latent TB without re-exposures will not be excluded.
- Previous treatment with any agent that targets the interleukin 23 p19 subunit specifically.
- Systemic treatment with prednisone in the last 2 weeks, or other systemic therapies or phototherapy for PRP within the past 4 weeks or 5 half-lives prior to baseline, whichever is longer. For biologic therapies, the specific washout periods used will be: etanercept <28 days; infliximab, adalimumab, ixekizumab, or alefacept <60 days; golimumab <90 days; secukinumab <5 months; ustekinumab <8 months; rituximab or efalizumab <12 months.
- Have a known allergy or hypersensitivity to any biologic therapy that would pose an unacceptable risk to the subject if participating in this study.
- Have or intend to have a live vaccine within 3 months prior to baseline or 12 months prior to baseline in the case of the BCG vaccine, or any live vaccine during the course of study or within 3 months after the last administration of study drug.
- Had any major surgery within 8 weeks prior to baseline or will require major surgery during the study that, in the opinion of the investigator, would pose an unacceptable risk to the subject.
- Presence of significant uncontrolled cerebrovascular, respiratory, hepatic, renal, gastrointestinal, endocrine, hematologic, neurologic, or neuropsychiatric disorders, or abnormal laboratory screening values that, in the opinion of the investigator, pose an unacceptable risk to the subject if participating in the study or of interfering with the interpretation of the data.

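### The protocol expects lasting benefit mainly in subjects without mutations, but the week-36 analysis is a single pooled mean that would rarely reveal relapse confined to the few CARD14 carriers

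*Combined protocol and SAP*

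**What the plan says.** Section 3.2.3 gives the reason for the last visit. Treatment might reset the immune response and "lead to long-term improvement in the disease, especially in subjects without genetic mutations". On follow-up it says: "Subjects will be monitored at 24 weeks (primary study endpoint) and then at 36 weeks to assess for sustained remission versus relapse". The endpoint is the mean PASI change between weeks 24 and 36.

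Section 3.2.4 says: "Genetic CARD14 mutations will be measured in study subjects and associated with treatment response to guselkumab". It cites gain-of-function mutations in "12.5% of individuals with sporadic PRP".

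Section 7.2.3 analyses the endpoint as one mean: "Sustained remission at week-36, measured by the mean change in PASI score from week-24 to week-36, will be analyzed for statistical significance", by a paired, two-tailed t-test. Genotype enters the clinical analyses once: "Treatment response, as measured by PASI 50, will be stratified by CARD14 germline mutations".

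On timing, section 3.2.3 reads "Sustained remission at week-36, 16 weeks after the last guselkumab dose", whereas section 5.1.10 places Visit 7, labelled week 36, 56 days (plus or minus 7) after the preceding visit, which is week 24.

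**The concern.** The protocol voices an expectation about durability that depends on mutation status, collects the genotype, and then gives durability an analysis that cannot look at it. The one genotype split uses PASI 50. That is improvement relative to baseline, so a subject can worsen considerably after week 24 and still count as a responder.

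If the expectation is right, carriers relapse once dosing stops and non-carriers hold. With only one or two carriers, the pooled test would probably be non-significant. That result could be reported as sustained remission although every carrier had relapsed.

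**Working it through.** **Inputs from the documents.** Planned n = 15 and two-sided alpha 0.05 (section 7.1); carrier rate 0.125 in sporadic PRP (section 3.2.4); one paired t-test on the week-24 to week-36 change (section 7.2.3).

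**Assumptions.** The documents give no SD for this change and no size of relapse. I use SD 4 to 8, the range of the section 7.1 table, and relapses of 8 to 20 PASI points in every carrier, with non-carriers unchanged on average. Positive values mean worsening.

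**The plan's own figure.** For n = 10, mean change 8 and SD 8, the noncentrality is (8/8) × √10 = 3.16 on 9 df, and two-sided power is 0.8031, as tabulated in section 7.1. That figure concerns the primary endpoint. None is given for week 36.

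**Number of carriers.**
- Expected: 15 × 0.125 = 1.9.
- None: 0.875^15 = 0.135.
- None or one: 0.135 + 15 × 0.125 × 0.875^14 = 0.424.
- Three or fewer: 0.89.

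**Shift of the pooled mean.** With k carriers relapsing by X, the mean is kX/15. For k = 2 it is 2 × 8/15 = 1.07 up to 2 × 20/15 = 2.67. Non-carriers hold 13/15 = 87% of the weight.

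**Test result without noise.** If non-carriers change by exactly 0 and carriers all relapse equally, X cancels and t = √(14k/(15 − k)) on 14 df:

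| Carriers | t | p |
|---|---|---|
| 1 | 1.00 | 0.33 |
| 2 | 1.47 | 0.16 |
| 3 | 1.87 | 0.08 |
| 4 | 2.26 | 0.04 |

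In this setting, relapse confined to one to three carriers cannot reach 0.05, whatever its size.

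**With noise, 2 carriers of 15** (simulation, 100,000 trials per setting; mean 95% CI half-widths):

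| SD | Relapse | Pooled half-width | Non-carriers only (n = 13) | Ratio | Significant |
|---|---|---|---|---|---|
| 4 | 8 | 2.7 | 2.4 | 1.13 | 8% |
| 4 | 10 | 2.9 | 2.4 | 1.23 | 9% |
| 4 | 20 | 4.5 | 2.4 | 1.88 | 6% |
| 8 | 8 | 4.6 | 4.7 | 0.98 | 6% |
| 8 | 10 | 4.8 | 4.7 | 1.01 | 7% |
| 8 | 20 | 5.8 | 4.7 | 1.23 | 8% |

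Over the same relapse range, the planned test is significant in about 3% to 5% of trials with one carrier and 8% to 19% with three.

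**A formal carrier versus non-carrier test.** With 2 against 13, the 95% half-width is 2.160 × SD × √(1/2 + 1/13) = 6.6 points at SD 4 and 13.1 at SD 8. Power for an 8-point difference is 0.68 and 0.23.

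**Timing.** Section 5.1.9 puts the week-24 visit 28 ± 4 days after the last injection. Adding the 56 ± 7 days of section 5.1.10 gives 84 days, at most 28 + 4 + 56 + 7 = 95. Sixteen weeks is 112 days, so the stated windows cannot reach it.

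**The case against.** The strongest reply is that endpoint and analysis agree. Section 3.2.3 defines a pooled mean change and section 7.2.3 tests exactly that. The remark about mutations is rationale, worded as a possibility, and neither the hypothesis nor any objective mentions it. This stands as far as it goes: no stated commitment is broken. But the protocol gives a reason for the visit, and the data to examine it will be in hand.

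The stratified PASI 50 analysis names no visit, so a week-36 version would be compatible with the text. It would still not measure change after week 24.

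A reader might infer more than the documents support:
- **That the pooled mean describes neither group.** It does not go that far: non-carriers hold 87% of the weight.
- **That pooling generally makes the interval much wider.** At SD 8 the ratio is only 0.98 to 1.23. Ratios approaching 1.9 need SD 4 and a relapse near 20 points.
- **That drug must still be active at week 36, because section 4.2 sets longer washouts for some antibodies** ("secukinumab <5 months; ustekinumab <8 months"). Six of the ten listed agents have washouts shorter than 112 days, these are eligibility rules for other drugs, and no half-life for guselkumab is given. The documents cannot settle it.
- **That the protocol claims drug-free remission.** It does not use that term.

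It is also fair that the low rate of significance is not cured by the fix, which adds no test, and that week-24 non-responders remain in either mean. Section 3.2.3 speaks of genetic mutations generally, so CARD14-negative may not mean free of every PRP-related mutation.

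**Conclusion.** The point holds in a limited form. The protocol's expectation about durability by mutation status has no matching analysis of the week-24 to week-36 change, and the pooled test would usually miss relapse confined to the one to three carriers likely to be enrolled. With two carriers it is significant in about 6% to 9% of trials. The non-carrier estimate suffers little: a shift of about 1.1 to 2.7 points and an interval about 1.0 to 1.9 times as wide.

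These sizes rest on the assumed SDs and relapse sizes, on every carrier relapsing while non-carriers stay flat on average, and on a 12.5% rate reported for sporadic disease. Familial cases are not excluded, so the carrier share could be higher. It could also be nil, in which case the split is empty.

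A non-significant pooled change is not evidence of sustained remission or an immune reset, with or without the split. Listing the endpoint as secondary in section 3.2.3 and exploratory in section 7.2.3 is an editorial mismatch: the plan has no testing hierarchy for it to disturb.

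**What to change.** In section 7.2.3, keep the pooled estimate and add a prespecified table, labelled descriptive:
- the week-24 to week-36 PASI change (mean, 95% CI) in subjects without a CARD14 mutation;
- each carrier's PASI at weeks 0, 24 and 36;
- no formal subgroup test.

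State that a non-significant pooled change will not be read as sustained remission or a reset, and that the result will be described as the PASI change over the actual interval since the last dose. Reconcile the Visit 7 window in section 5.1.10 with the week-36 label and the interval in section 3.2.3. Use one endpoint tier in sections 3.2.3 and 7.2.3.

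The cost is some wording and one table from data already collected. Specifying it now matters because section 7.2 has the principal investigator analysing open-label data throughout, so a split added later could look data-driven. The downsides are that the non-carrier estimate rests on about 13 subjects, carriers are only described, and CARD14 status may not capture all relevant mutations. The table also does not supply a per-subject definition of remission or relapse, which the plan lacks.

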7. STATISTICAL CONSIDERATIONS

7.1. Sample Size Computation and Power Analysis

This is a pilot study with no published baseline data; thus a power analysis was performed with the following rough assumptions. With measurement of the mean paired difference in PASI score before and after treatment of a minimum of 10 subjects, we would have 80% power at the 0.05 level to detect a mean within-subject change of 8-points when the standard deviation is 8-points. Due to the uncertainty inherent with a pilot study, the goal number of subjects with PRP who will be recruited for the study is 15.

				Mean Change	Standard
Power (1-ß)	Sample Size	а	ß	in PASI	Deviation
0.9998	10	0.05	0.0002	-8	4
0.9940	10	0.05	0.0060	-8	5
0.9621	10	0.05	0.0379	-8	6
0.8942	10	0.05	0.1058	-8	7
0.8031	10	0.05	0.1969	-8	8
0.9873	10	0.05	0.0127	-6	4
0.9203	10	0.05	0.0797	-6	5
0.8031	10	0.05	0.1969	-6	6
0.6755	10	0.05	0.3245	-6	7
0.5620	10	0.05	0.4380	-6	8

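### Response by CARD14 status is compared only on dichotomised PASI 50; the cut discards about one third to two thirds or more of the information in a comparison with about 2 expected carriers

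*Combined protocol and SAP*

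**What the plan says.** Section 3.2.4 lists as an exploratory endpoint "Treatment response, as measured by PASI 50, stratified by the presence or absence of germline CARD14 mutations". Section 7.2.3 keeps the same measure: "Treatment response, as measured by PASI 50, will be stratified by CARD14 germline mutations". It says "The proportion of subjects with a PASI 50 response with and without CARD14 mutations will be reported" and that the two proportions will be tested with an unpaired, two-sided t-test. Neither section fixes the time point of PASI 50 for this comparison.

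The primary analysis in section 7.2.1 leaves PASI change on its continuous scale: "Mean improvement from baseline PASI at week-24 will be analyzed for statistical significance using a paired, two-tailed" Student's t-test. PASI is scored at baseline and at every later visit, and saliva for genotyping is taken at baseline (sections 5.1.4 to 5.1.10), so both variables are already collected. The synopsis describes the aim more broadly, as relating improvement to germline mutations.

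On numbers, section 3.2.4 reports that CARD14 gain-of-function mutations were found in familial cases "as well as 12.5% of individuals with sporadic PRP", and section 7.1 says "the goal number of subjects with PRP who will be recruited for the study is 15". No power is claimed for the CARD14 comparison.

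**The concern.** A yes/no cut treats a subject who improves by 55% like one who clears completely, and a subject who improves by 45% like one who does not change. A difference between carriers and non-carriers that lies wholly above or wholly below 50% cannot be seen. With so few carriers, each one's result should be used in full.

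The question is also tied to the trial's rationale: section 3.2.3 suggests that lasting benefit may be likelier in subjects without a mutation. The point here is the outcome scale. Replacing the t-test on 0/1 data with an exact test of proportions would leave the loss in place.

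**Working it through.** **Inputs from the documents.** Target n = 15; carrier frequency 12.5% (section 3.2.4, sporadic cases); SD of PASI change 8 points and two-sided alpha 0.05 (section 7.1).

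**Assumptions.** The PASI 50 rate in non-carriers is not given and is varied from 50% to 95%. Response is taken as normal with equal SD in both groups, and the cut is taken on the same scale as the shift (PASI 50 is in fact a percentage change). The carrier difference is set at 1 SD = 8 points.

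**1. The plan's own figure.** Section 7.1 claims, "after treatment of a minimum of 10 subjects", "80% power at the 0.05 level to detect a mean within-subject change of 8-points when the standard deviation is 8-points". For a two-sided paired t-test with 9 df and noncentrality (8/8)·√10 = 3.16, the power is 0.8031. This equals the tabulated value, and the other nine rows agree to within 0.0001. There is no corresponding figure for CARD14.

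**2. Expected carriers.** 15 × 0.125 = 1.9. P(0) = 0.875^15 = 0.135. P(1) = 15 × 0.125 × 0.875^14 = 0.289. P(0 or 1) = 0.424.

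**3. Information lost by the cut (large sample).** The relative efficiency of a dichotomised normal outcome is φ(z_p)² / [p(1−p)], where p is the response rate. At p = 0.90 this is 0.1755² / 0.09 = 0.342, a loss of 66%.

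| Response rate | Efficiency | Loss |
|---|---|---|
| 50% | 0.637 | 36% |
| 75% | 0.539 | 46% |
| 80% | 0.490 | 51% |
| 90% | 0.342 | 66% |
| 95% | 0.224 | 78% |

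**4. Power with 2 carriers and 13 non-carriers.** For a continuous two-sample t-test with 13 df, the noncentrality for 1 SD is √(2 × 13/15) = 1.32 and the power is 23%. It is 9% for 4 points, 45% for 12 and 68% for 16; 80% power needs about 18.5 points. The binary tests were enumerated exactly over all outcomes, with the carrier response rate set to Φ(z_p ∓ 1).

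| Non-carrier PASI 50 rate | Continuous t | Planned 0/1 t, carriers worse by 1 SD | Planned 0/1 t, carriers better by 1 SD | Fisher, worse | Fisher, better |
|---|---|---|---|---|---|
| 50% | 23% | 3% | 3% | 0.1% | 0.1% |
| 60% | 23% | 10% | 0.8% | 0.8% | 0.0% |
| 75% | 23% | 24% | 0.4% | 5% | 0.0% |
| 90% | 23% | 27% | 0.6% | 9% | 0.0% |

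The 0/1 t-test figures count complete separation (0/2 against 13/13) as significant, although the statistic is then undefined. In the 90% row, carriers worse, that outcome has probability 0.389² × 0.9^13 = 0.151 × 0.254 = 0.038. Counting it as not significant lowers 27% to about 23%.

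At 2 SD with carriers worse, the continuous test has 68%. The 0/1 t-test has 4%, 49% and 66% at non-carrier rates of 50%, 75% and 90%; Fisher has 0.2%, 10% and 36%.

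**5. What an exact test of proportions can detect.** There are C(15,2) = 105 ways to place 2 carriers. If both carriers fail, Fisher p is 1/105 = 0.0095 with 13/13 non-carriers responding, 3/105 = 0.029 with 12/13, and 6/105 = 0.057 with 11/13. Only near-complete separation (or its mirror image) reaches 0.05. If 7 or more of the 13 non-carriers respond, no result can show that carriers do better.

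**6. Limits of a permutation test on the full scale.** With 2 carriers, the smallest two-sided rank p is 2/105 = 0.019. With 1 carrier, the smallest possible p is 1/15 = 0.067, above 0.05 whatever the data. With no carriers there is no comparison.

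**The case against.** The comparison is exploratory, in a pilot study, with no power claimed. PASI 50 is a recognised measure of improvement that the plan already uses among its secondary endpoints, so using it here is a choice and not an error. That is fair, and it sets the severity.

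The stronger objection is that carrier numbers, not the cut, are the main limit. With a 42% chance of at most one carrier, and about 23% power for 8 points even on the continuous scale, no choice of outcome makes this a reliable test. This stands. It argues for estimation and display rather than for another p-value.

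A reader might infer that the cut always removes most of the information. The documents do not support that: the loss passes one half only at response rates of about 80% or more, and no PASI 50 rate in PRP is given. The only benchmark, in section 1.1, is marked improvement in 90% of case reports of a different agent, which is not PASI 50.

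A reader might also infer that the continuous scale always gains much power. Against Fisher it does at 1 SD, but the plan specifies a t-test on the 0/1 variable. When carriers respond worse and non-carrier response is 75% to 90%, that test has 24% to 27% power, as much as the continuous test. Its type I error is about 5.5% with 2 carriers and 90% response, close to nominal, though about 9% with 3 carriers.

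**Conclusion.** The point holds as a modest improvement. Sections 3.2.4 and 7.2.3 confine the CARD14 comparison to PASI 50 although continuous PASI change is already measured. The large-sample loss is 36% to 78% of the information for response rates of 50% to 95%. The clearest cost arises if carriers respond better: the planned test then has 0.4% to 3% power against about 23% on the continuous scale. If carriers respond worse, the planned test ranges from about 3% to 27% and sometimes matches the continuous one. Fisher stays under 10% in either direction at this effect size.

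These powers rest on exactly 2 carriers of 15, SD 8 in both groups, a normal response and an assumed 8-point difference. Familial cases would raise the carrier count. The documents do not support calling the plan invalid here, or saying that the change would make the comparison adequately powered.

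**What to change.** In sections 3.2.4 and 7.2.3, define the CARD14 analysis as the difference between carriers and non-carriers in week-24 PASI improvement, choosing percentage or absolute change in advance. Report it with a 95% confidence interval and a plot of each subject's value by CARD14 status. Keep the PASI 50 counts by status as description, without a test. An exact permutation p-value may be added as secondary, only with at least 2 carriers; with 0 or 1 carrier, report descriptively only.

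The cost is a change of wording, with no new data or visits. Percentage change is noisier in subjects with low baseline PASI, which the individual plot will show. Power stays low on any scale, so the report should present the interval as the result.
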